7.8.2 Securing Blinding and Randomization Information

Randomization lists will be maintained in a secured area by the individual(s) responsible for maintaining the blind. During site visits, the Clinical Research Associate will check the occluded labels (or disclosure envelopes) to ensure that they are intact and in a secure, yet accessible, location for study personnel. If any of the occluded labels or disclosure envelopes is opened, the Clinical Research Associate will verify that the Principal Investigator, the Independent Safety Monitor of the study and the NIAID Medical Officer have been notified and that a written account has been completed and forwarded to the above individuals.

7.8.3 Requirements for Unblinding

This study may be unblinded only for safety reasons or only if the study information is needed for an interim or final analysis as described below.

If a clinically significant event occurs and knowledge of treatment assignment is required, the blind may be broken. Unblinding must be approved by the Independent Safety Monitor unless an immediate life threatening condition has developed and the Independent Safety Monitor is not accessible. In all cases of unblinding, the NIAID Medical Officer will be notified immediately.

Unblinding the study because of an approved interim analysis, final analysis, or study termination (as described in section 8.1) will require written approval from NIAID.

7.8.4 Documenting an Unblinding

Any unblinding (opening of a label or disclosure envelope) will require a full written account of the event(s) that necessitated the unblinding of the treatment assignment for an individual participant(s). This account will be made in the participant(s) study file and in the final study report and will include the reason(s) for the unblinding,

the name of the Independent Safety Monitor who was notified and approved the unblinding, the names of the individuals unblinded, and the date and time the unblinding occurred.

8 SAFETY PROCEDURES

8.1 Stopping Rules

8.1.1 Study Stopping Rules

Study enrollment and study procedures will be suspended pending expedited review of all pertinent data by the Partners institutional review board (IRB), the ISM, the DAIT DSMB, and the NIAID Medical Officer, if a participant at any time or in any group develops a severe or life threatening adverse event such that he or she requires an emergency room visit, hospitalization, or an unexpected (non-allergy-related) hospitalization or death.

Study enrollment will be suspended pending expedited review of all pertinent data by the DSMB if any of the following occur:

- Any death related to peanut OIT dosing
- More than one event of severe systemic anaphylaxis, defined by any of the following: hypoxia (cyanosis or SpO2 <92% during reaction), documented hypotension (>30% fall from baseline systolic BP), neurological compromise (confusion, loss of consciousness), or incontinence after ingestion of peanut at any stage of the protocol
- More than 3 participants requiring more than 2 injections of epinephrine during dosing of the peanut product.

All above events will be reported immediately to the Partners IRB and to the FDA, the DSMB, and the NIAID Medical Officer. The study will not resume until approval is given by the FDA and IRB, the DSMB, and NIAID.

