4.3 Participant Withdrawal Criteria

Participants may be terminated early from the study for the following reasons:

- The participant elects to withdraw consent from all future study activities, including follow-up.
- The participant is "lost to follow-up" (i.e., no further follow-up is possible because attempts to reestablish contact with the participant have failed).
- The participant dies.
- The participant develops a medical condition or is started on new medication(s) not previously mentioned in the list of prohibited medications that, in the opinion of the investigator, may pose additional risks from participation in the study, may interfere with the participant's ability to comply with study requirements or that may impact the quality of the data obtained from the study.
- The participant meets any of the individual stopping rules as delineated in section 8.
- Dose adjustment required more than twice due to missed at-home dosing.
- Rescheduling of two consecutive, or more than four total dose escalation visits.

Participants with early termination from this study will not be replaced.

5 INVESTIGATIONAL PRODUCT(S) / INTERVENTION MATERIAL(S), OTHER STUDY PRODUCTS (CONTROLS/PLACEBOS)

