7.7.2 Immunotherapy Administration

Drug product will be prepared in the MGH CRC as described in Section 5.3. Participants will ingest daily dose of immunotherapy mixed with one of a few vehicle foods they may choose and which they will provide. The oral immunotherapy procedure consists of three phases: Modified Rush, Build Up, and Maintenance.

7.7.2.1 Modified Rush The modified rush procedure begins with 0.1 mg peanut protein-containing peanut powder or equivalent placebo, stirred in a vehicle food, approximately doubling the dose every 30 minutes until a maximum of 6 mg is tolerated (cumulative dose of 12 mg; Figure 15.2). Available vehicle foods will include rice milk, soymilk, mint chocolate mousse, or applesauce, depending on the participant's other allergies and p s. The MGH CRC will prepare all doses. This visit will occur within 2 weeks after the completion of DCPCFC1.

Participants will not have active wheezing or a current flare in atopic dermatitis. If symptoms occur preventing escalation to 6 mg, the highest tolerated dose (at least 1.5 mg) will be accepted as the dose for further escalation. Participants must tolerate at least 1.5 mg as a final dose to remain in the study.

Participants may develop symptoms during the initial escalation. For isolated oral or pharyngeal pruritus, the action should be to continue the normal dosing in 30 minutes. If symptoms are not limited to isolated oral or pharyngeal pruritus, the investigator's judgment will be required to determine the best course of action with possible actions being the following:

- 1. Extend time interval between dosing (up to an additional 30 minutes) and advance forward
- 2. Return to previously tolerated dose (i.e., repeat of last tolerated dose) then advance forward
- 3. Discontinue protocol and define the starting Build Up dose as the previously given dose

The Modified Rush procedure will be immediately stopped and the participant promptly treated for objective signs and symptoms as indicated in Figure 15.4, consistent with the 2010 NIAID-sponsored expert guidelines for the diagnosis and management of food allergies [?].

For a completed initial escalation protocol with no symptoms or only mild symptoms, subjects should have a 2-hour post-protocol observation period. For moderate to severe symptoms, the observation period will be extended based on the participants symptoms and the treatment regimen required to stabilize the participant.

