8.1.2 Individual Stopping Rules

Safety of the participant will remain of primary importance. Any participant who develops severe systemic anaphylaxis, defined by any of the following: hypoxia (cyanosis or SpO2 <92% during reaction), documented hypotension (systolic BP>30% fall from baseline systolic BP), neurological compromise (confusion, loss of consciousness), or incontinence after ingestion of peanut, significant hypotension during any stage of the protocol, and/or requires more than 2 injections of epinephrine during any administration of the peanut product will be withdrawn from the study.

Participants who are ingesting daily maintenance dose of peanut will be dropped from the study if they are having NCI-CTCAE grade 2 or higher gastrointestinal, respiratory, or dermatologic symptoms at home within 2 hours of taking the daily dose of peanut for 5 or more consecutive days. The determination of symptoms and their relativity to the daily dose rather than a concurrent illness must be evaluated by the PI and thought to be related to the peanut before being dropped from the study. Recurrent symptoms for 5 or more consecutive days that are occurring more than 2 hours after the daily IT dose may prompt an individual being dropped, if the investigator believes that they are related to IT dosing.

Mild or moderate adverse events such as nausea, vomiting, increased asthma symptoms, allergic dermal reactions, or fever will cause the procedure on the individual patient to be discontinued, will be reported in the required timely manner to the Partners IRB, but will not automatically cause the study to be halted. Each participant will be treated

for worsening asthma, atopic dermatitis, or suspected EoE symptoms and removed from the study when deemed necessary by the PI.

8.1.3 Early Discontinuation of Investigational Product(s) / Intervention(s) with continued study participation / follow-up

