15.4 Treatment Table

Signs / Symptoms	Treatments
LUNG: wheeze, cough	 Epinephrine, IM; auto-injector or 1:1,000 solution IM (anterior-lateral thigh) 0.3 mg epinephrine autoinjector, IM (anterior-lateral thigh) OR Epinephrine (1:1,000 solution) (IM), 0.01 mg/kg per dose; maximum dose, 0.5 mg per dose (anterior-lateral thigh) H1 antihistamine: diphenhydramine 1 to 2 mg/kg per dose Maximum dose, 50 mg IV or oral (oral liquid is more readily absorbed than tablets) Bronchodilator (b2-agonist): albuterol MDI (child: 4-8 puffs; adult: 8 puffs) or
	 Nebulized solution (child: 1.5 ml; adult: 3 ml) every 20 minutes or continuously as needed 4. Supplemental oxygen therapy 5. Corticosteroids Prednisone at 1 mg/kg with a maximum dose of 60 to 80 mg oral or Methylprednisolone at 1 mg/kg with a maximum dose of 60 to 80 mg IV
HEART: hypotension, cardiovascular collapse	 Epinephrine, IM; auto-injector or 1:1,000 solution Same as above H1 antihistamine: diphenhydramine Same as above Corticosteroids Same as above H2 antihistamine: ranitidine 1 to 2 mg/kg per dose Maximum dose, 75 to 150 mg oral or IV Vasopressors (other than epinephrine) for refectory hypotension, titrate to effect Glucagon for refractory hypotension, titrate to effect Child: 20-30 mg/kg Adult: 1-5 mg Dose may be repeated or followed by infusion of 5-15 mg/min Atropine for bradycardia, titrate to effect IV fluids in large volumes if patient presents with orthostasis, hypotension, or incomplete response to IM epinephrine Place the patient in recumbent position if tolerated, with the lower extremities elevated

Signs / Symptoms	Treatments
THROAT: hoarse, swelling	 Epinephrine, IM; auto-injector or 1:1,000 solution Same as above H1 antihistamine: diphenhydramine Same as above Corticosteroids Same as above Consider H2 antihistamine: ranitidine Same as above
SKIN: hives, swelling, pruritus	 H1 antihistamine: diphenhydramine Same as above Consider Epinephrine, IM; auto-injector or 1:1,000 solution Same as above Consider H2 antihistamine: ranitidine Same as above
GUT: vomiting, nausea, diarrhea, pain or discomfort	 H1 antihistamine: diphenhydramine Same as above Consider Epinephrine, IM; auto-injector or 1:1,000 solution Same as above Consider H2 antihistamine: ranitidine Same as above
MOUTH: hives, swelling, oral pruritus	 H1 antihistamine: diphenhydramine Same as above Consider Epinephrine, IM; auto-injector or 1:1,000 solution Same as above Consider H2 antihistamine: ranitidine Same as above

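### After repeated severe anaphylaxis treated without an emergency room visit or admission, Section 8.1.1 suspends enrolment but does not stop dosing in other participants

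*Combined protocol and SAP*

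**What the plan says.** Section 8.1.1 (Study Stopping Rules) of the combined protocol and SAP has two trigger paragraphs and a closing paragraph.

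- Paragraph 1: "Study enrollment and study procedures will be suspended pending expedited review of all pertinent data". It is triggered by a single participant with a severe or life-threatening adverse event such that he or she "requires an emergency room visit, hospitalization, or an unexpected (non-allergy-related) hospitalization or death". The reviewers are the IRB, the Independent Safety Monitor (ISM), the DSMB and the NIAID Medical Officer.
- Paragraph 2: "Study enrollment will be suspended pending expedited review of all pertinent data by the DSMB if any of the following occur". The list is a death related to OIT dosing, more than one severe systemic anaphylaxis at any stage, or more than 3 participants needing more than 2 epinephrine injections.
- Closing paragraph: it refers back to all the events above it, requires immediate reporting, and ends "The study will not resume until approval is given by the FDA and IRB, the DSMB, and NIAID".

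Section 8.1.2 withdraws any participant who has severe systemic anaphylaxis or needs more than 2 injections. It adds that mild or moderate events end the procedure for that individual "but will not automatically cause the study to be halted".

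**The concern.** The sentence that sets the action under paragraph 2 names enrolment only. The sentence that sets the restart speaks of the study as a whole. Staff facing a second severe reaction could reasonably follow either one. Under the first, participants already randomised keep taking daily doses at home and keep attending for scheduled increases while the DSMB reviews. Under the second, dosing stops.

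A study-level stopping rule exists to protect participants who have not yet reacted. In this trial they are exposed through dosing, and a pause in enrolment does not change that. The rule should be clear before such an event occurs.

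**Working it through.** The plan states no figure to reproduce here. The check is a comparison of the text, followed by simple exposure arithmetic.

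**Step 1. Scope of each rule (8.1.1).**

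| | Event | Action stated |
|---|---|---|
| Paragraph 1 | One severe or life-threatening event needing an ER visit or admission | Enrolment and procedures suspended |
| Paragraph 2 | At least 2 severe systemic anaphylaxis events, or at least 4 participants each needing more than 2 injections | Enrolment suspended |
| Closing | All of the above | Restart needs FDA, IRB, DSMB and NIAID approval |

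**Step 2. Which events fall under paragraph 2 alone.**

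- *Severe anaphylaxis leading to an ER visit or admission.* Paragraph 1 already suspends procedures at the first such event, so there is no gap.
- *Two or more severe anaphylaxis events, or repeated use of more than 2 injections, with no ER visit or admission.* Only paragraph 2 applies. Enrolment stops, and nothing says whether enrolled participants keep dosing.

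The death bullet is left out of the gap, because paragraph 1 also mentions death.

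**Step 3. Whether the second case can occur.** The paragraph 2 definitions require neither an ER visit nor admission. SpO2 below 92%, a systolic fall of more than 30%, confusion or incontinence is enough. The protocol equips the research centre to treat serious reactions:

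- An IV is placed and a physician is present at DBPCFC1 and the Modified Rush (7.4.1, 7.4.2).
- The treatment table (15.4) includes "IV fluids in large volumes if patient presents with orthostasis, hypotension, or incomplete response to IM epinephrine".
- The Modified Rush text (7.7.2.1) says "For moderate to severe symptoms, the observation period will be extended based on the participants symptoms and the treatment regimen required".
- In the anaphylaxis grading (8.2.3.1), transient hypotension is a Grade 3 feature, for which hospitalisation is only possible.

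The case is therefore narrow but not empty. The documents give no frequency for it.

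**Step 4. Ordering of the two rules.** One severe event with an ER visit stops procedures. Two or more severe anaphylaxis events treated on site do not, as written. Whether dosing stops then depends on where care was given, not on how severe or how frequent the reactions were.

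**Step 5. Exposure if dosing continues.** The review length is not stated, so 1, 2 and 4 weeks are assumed. Dosing is daily and Build Up increases are every 14 days (7.7.2.2).

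| Assumed review | Doses per participant | Scheduled increases per Build Up participant |
|---|---|---|
| 7 days | 7 | 0 or 1 |
| 14 days | 14 | 1 |
| 28 days | 28 | 2 |

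Over the 22 increases in 15.3, the smallest is (4000 - 3575)/3575 = 11.9%, the largest is (25 - 12)/12 = 108.3%, and the median is 25%. These figures describe exposure; they are not risk estimates. The number of participants on dosing at the time is unknown.

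**Step 6. After enrolment is complete.** Dosing runs from the Modified Rush (Day 42) to DBPCFC2 (Day 434): 434 - 42 = 392 days on schedule. If the last participant has been enrolled, paragraph 2 read literally has nothing left to suspend for that whole period.

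**The case against.** A reader might infer that 8.1.1 flatly contradicts itself. The text does not go that far. The closing sentence orders no stop. It sets a restart condition, and paragraph 1's full suspension gives it a natural referent. Section 8.1.2 says only that mild or moderate events do not automatically halt the study, which suggests that graver ones do but does not settle paragraph 2's scope. What stands is that the action under paragraph 2 is enrolment only and the restart sentence does not repair that.

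Other provisions reduce the exposure.

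- The features listed in paragraph 2 overlap with Grade 4 anaphylaxis, where 8.2.3.1 calls hospitalisation probable, so many such events would reach paragraph 1.
- The treatment table does not say that care ends on site, and 7.7.2.1 also requires the procedure to be stopped and the participant treated.
- The affected participant is withdrawn.
- For an SAE, the NIAID Medical Officer and the ISM are notified within 24 hours and discuss the impact on the study with the investigator within another 24 hours (8.2.4.1).

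These points narrow the gap but do not close it. Withdrawal protects only the person who reacted, and SAE notification prompts discussion without ordering a hold.

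Four further inferences are tempting and not supported.

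- *That the protocol has no restart rule.* Sections 5.6.2, 7.7.2.2 and 7.7.2.3 send anyone who misses four or more days back to the research centre for re-escalation from 50%.
- *That long delays can be calculated from the stepped resumption schedule.* That schedule is written for reactions and acute infections (7.7.2.2, 8.2.2.4), not for a gap in dosing.
- *That a hold would wreck Build Up.* Maintenance may start at the highest dose tolerated by week 50, provided it is at least 600 mg (7.7.2.3).
- *That the ISM is shut out.* The ISM reviews all SAEs (8.2.1.6).

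**Conclusion.** The concern holds as a gap in scope. For repeated severe anaphylaxis, or repeated use of more than 2 epinephrine injections, managed without an ER visit or admission, 8.1.1 as written lets dosing and increases continue in other participants during review. It does nothing once enrolment is complete.

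The size is 7 to 28 further doses and 0 to 2 scheduled increases per Build Up participant, under an assumed review of 1 to 4 weeks, plus up to 392 days in which the trigger is empty for the last participant enrolled. This rests on reading paragraph 2 literally and on such events being treated without an ER visit or admission, which the protocol allows but does not quantify. It should be fixed: the case is narrow, but it concerns participant safety and the correction is small.

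**What to change.** - In paragraph 2 of 8.1.1, extend the suspension from enrolment to enrolment and study procedures, including OIT dosing and dose escalation. This matches paragraph 1 and gives the closing sentence a clear meaning.
- In 4.3, with a cross-reference in 5.6.2, state that doses and visits missed because of a study hold do not count toward withdrawal. One of the criteria is "Rescheduling of two consecutive, or more than four total dose escalation visits", and it has no exception for a hold. This is a safeguard: one hold would cause at most one missed-dose adjustment, against a limit of more than two, and 4.3 says that participants may, not must, be terminated.
- State that restart follows the existing research-centre procedure for gaps of four or more days (5.6.2). Every hold length assumed above is at least 7 days, so it would apply.

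The cost is a short protocol amendment with review by the IRB, ISM, NIAID and FDA, and no running cost unless a trigger occurs. If one does, each participant then on dosing needs a re-escalation visit at the research centre, and the schedule slips by the length of the hold plus re-escalation.

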8.1.2 Individual Stopping Rules

Safety of the participant will remain of primary importance. Any participant who develops severe systemic anaphylaxis, defined by any of the following: hypoxia (cyanosis or SpO2 <92% during reaction), documented hypotension (systolic BP>30% fall from baseline systolic BP), neurological compromise (confusion, loss of consciousness), or incontinence after ingestion of peanut, significant hypotension during any stage of the protocol, and/or requires more than 2 injections of epinephrine during any administration of the peanut product will be withdrawn from the study.

Participants who are ingesting daily maintenance dose of peanut will be dropped from the study if they are having NCI-CTCAE grade 2 or higher gastrointestinal, respiratory, or dermatologic symptoms at home within 2 hours of taking the daily dose of peanut for 5 or more consecutive days. The determination of symptoms and their relativity to the daily dose rather than a concurrent illness must be evaluated by the PI and thought to be related to the peanut before being dropped from the study. Recurrent symptoms for 5 or more consecutive days that are occurring more than 2 hours after the daily IT dose may prompt an individual being dropped, if the investigator believes that they are related to IT dosing.

Mild or moderate adverse events such as nausea, vomiting, increased asthma symptoms, allergic dermal reactions, or fever will cause the procedure on the individual patient to be discontinued, will be reported in the required timely manner to the Partners IRB, but will not automatically cause the study to be halted. Each participant will be treated

for worsening asthma, atopic dermatitis, or suspected EoE symptoms and removed from the study when deemed necessary by the PI.

8.1.3 Early Discontinuation of Investigational Product(s) / Intervention(s) with continued study participation / follow-up

8.1.3.1 Unscheduled Termination In accordance with the Declaration of Helsinki, patients have the right to withdraw from the study at any time for any reason. Participants may withdraw with or without medical advice. The investigator also has the right to withdraw participants from the study. Participants will be removed from the study for the following reasons: adverse experience, intercurrent illness or medication that in the judgment of the investigator may place the participant at risk, request of the investigator or participant for administrative or other reasons, protocol violation, determination that the participant is non-compliant or has unreliable behavior. Withdrawal from this study will have no impact on the future care of the participant at the Massachusetts General Hospital or any of its affiliated hospitals or health clinics.

8.1.4 Follow-up after early study termination

Participants who are prematurely terminated from the study will be followed to monitor safety for a minimum of 30 days or until resolution of the disqualifying event whichever is longer or until the Independent Safety Monitor, the NIAID Medical Officer and the Principal Investigator determine that the follow-up is complete.

